## 4.6.7 Approach to Management of Hypercalcemia and Secondary Hyperparathyroidism

Clinicians will manage hypercalcemia and secondary hyperparathyroidism as they do in usual clinical care, for example, by altering the binder regimen to reduce calcium intake, or using calcimimetics or vitamin D analogs to lower PTH.

## 4.7 Dialysis Provider Staff Roles

## 4.7.1 Role of Dietitians in Implementing HiLo Interventions in Facilities

Dietitians at dialysis units will be the on-the-ground personnel who will implement the HiLo protocols for phosphate management. The decision to have dietitians implement the protocols is based on multiple considerations:

- 1. Dietitians are employed by dialysis organizations, are present in all dialysis units, and usually serve as the primary decision makers for titration of phosphate-related treatments. Relying on clinical personnel to implement the trial intervention is consistent with the goals of pragmatic trials.
- 2. The HiLo phosphate algorithms will feel "natural" to both dietitians and patients. Dietitians have well established relationships with the patients who will participate in HiLo, they see them in the dialysis unit at least monthly, and are comfortable discussing phosphate management with them. The existing rapport between dietitians and patients will facilitate adherence to the interventions.
- 3. Dietitians are among the most motivated caregivers on dialysis teams. Anecdotally, they are often the most committed and scientifically inquisitive members of care teams, constantly seeking better approaches to enhance patient care in general, and diet and nutrition in particular, including phosphate management. To fully engage dietitians in the design and conduct of HiLo, DCRI will: (1) recruit 2 dietitian representatives to the HiLo Steering Committee to provide input into design and implementation; (2) identify a group of dietitians who will serve as local champions for HiLo and interact directly with dietitians at the units within their respective regions; and (3) drive interest among dietitians by having a HiLo presence at the DaVita and DCI national meetings and distributing HiLo newsletters throughout the conduct of the trial. DCRI will hold regular conference calls during the planning and conduct of the trial with participating dietitians for training updates and to review protocol adherence using a strategy of friendly competition across centers to maximize intervention fidelity. DCRI has initiated discussions with our dialysis partners about methods for recognizing and incentivizing participating dietitians.

## 4.7.2 Role of Treating Nephrologists

Although dialysis facilities will be randomized to high or low serum phosphate targets, the specific phosphate binding medications will be prescribed by the treating nephrologist(s) thus allowing for individualization of the prescription based on other considerations. Also consistent with standard practice, patients can have input into the prescribed medications through discussions with the treating nephrologist(s).

Participants may be discontinued from their study arm at the discretion of the dialysis provider physician. These participants will continue to be followed and will be included in the intent-to-treat analyses.

## 4.8 Adherence

In accordance with the clinical monitoring plan the DCRI will continuously monitor serum phosphate and remediate deviations from targets using webinars first and then in-person training visits, if needed. Sites will be notified by the DCRI whenever point-of-care serum phosphate measurements are repeatedly in the "action required" range; such notifications will be linked to a reminder of the facility's treatment group assignment and the facility's serum phosphate goals.

## 5. STUDY PROCEDURES

All of the HiLo Trial processes will be described in detail in the Manual of Procedures (MOP). The MOP will include trial activities occurring at the dialysis facilities, dialysis provider organization data warehouses, and the DCC at DCRI. The DCC is responsible for maintaining the manual and any associated documents, and will ensure that all relevant collaborators are informed about study procedures.

## 5.1 Facility Selection

In aggregate, our partnering dialysis provider organizations offer >3000 individual freestanding dialysis facilities to choose from in order to assemble a final roster of participating sites in HiLo. DCRI will work with our partners from the dialysis provider organizations to develop a strategy to select a suitable roster of dialysis facilities for HiLo; general considerations will include:

- Regional diversity across the US to maximize generalizability;
- Stability of candidate facilities, e.g. to exclude those with a dwindling census that could close;
- Willingness of medical directors, facility managers and dietitians to endorse the clinical equipoise that justifies HiLo and adopt either serum phosphate target for their patients;
- While provider organizations will support HiLo, facility managers should endorse the suitability of their dietitians to participate in training and regularly scheduled teleconferences throughout the duration of HiLo;
- Facility dietitian comfort with the different phosphate targets and willingness to implement the trial procedures and attend training and teleconferences throughout the duration of HiLo.

## 5.2 Participant Identification

Patients receiving care at participating dialysis facilities who meet the eligibility criteria will be identified through the electronic data systems of the dialysis provider organizations by the HiLo Trial Information Technology (IT) teams at the provider organizations. A unique research participant identifier (PID) for each participant will be generated. The PID will not be related to the patient's medical record number or any other identifier. Each dialysis provider organizations will maintain the key to the unique identifiers for participants enrolled from their organizations. The keys to the unique identifiers will not be transmitted to the DCRI. During the data extraction process, all personal identifiers will be replaced by the PID.

## 5.3 Participant Enrollment

Since HiLo includes a phosphate target that differs from current practice guidelines, the greater-than-minimal-risk research requires individual-level consent. HiLo initially used a cluster-randomized design in which participating dialysis centers were randomized to either the intervention or control arm. After completing enrollment in 30 dialysis units (14 Hi and 16 Lo sites), there was concern for biased enrollment. Therefore, the remainder of the trial will utilize individual-level randomization to ensure that arm assignment does not influence patients' willingness to participate. Patients enrolled in the cluster-randomized design will remain in the study through completion. For the individual randomized phase, the HiLo study will randomize approximately 3,800 additional participants (1,900 per arm).

## 5.3.1 Informed Consent

The trial will require that participants provide informed consent because the research poses greater than minimal risk. Electronic consent (eConsent) is rapidly becoming a new standard to improve efficiency, effectiveness and compliance of the informed consent process. Leveraging DCRI experience in other pragmatic trials, the study team will create an eConsent form and study educational materials that will be available at all participating dialysis facilities and also contain links to centralized clinical experts at DCRI that will be available to engage potential participants and answer their questions.

## 5.3.2 HIPAA Authorization

HIPAA Authorization forms will be obtained with informed consent.

## 5.4 Data Collection and Tracking

The electronic data systems of the dialysis provider organizations contain detailed clinical information from every dialysis treatment and the results of laboratory tests and hospitalization dates. These data are maintained in central electronic data warehouses. For HiLo, a pre-specified subset of data elements will be extracted from the central data warehouses and securely (encrypted) transferred to the DCRI database at regular intervals. No laboratory studies will be performed specifically for the trial. The following data elements will be obtained from clinical care data for all trial participants at the indicated frequency:

## Demographic and comorbidity data at study entry:

- Dialysis facility zip code
- Age
- Sex
- Race
- Ethnicity
- Height
- Weight
- Dialysis vintage
- Co-morbid illnesses noted on admission to the dialysis facility (ICD-9/10 codes)
- Cause of end-stage renal disease

For patients who decide not to participate in the trial, de-identified demographic and comorbidity data will be transmitted to the DCRI to allow comparison of characteristics of participating and non-participating patients.

#### Dialysis treatment data:

- Dialysis adequacy, single pool Kt/V, modality change: all available data
- Pre-dialysis and post-dialysis weights: every session
- Vascular access type (presence or absence of catheter): once per month

#### Laboratory data: monthly

In alignment with usual practice, all values available for the following laboratory test results will be made available to the DCRI by electronic data transfer on a monthly basis.

- Hemoglobin
- Albumin
- Calcium
- Phosphate
- Protein catabolic rate
- Serum ferritin
- Transferrin saturation

#### Laboratory data: once every 3 months

Intact parathyroid hormone

#### Hospitalizations data: all

#### Medications: all

All available data on medications will be made available to DCRI by electronic data transfer on a monthly basis, including but not limited to:

- Phosphate binders
- Activated vitamin D
- Home medications
- Calcium
- Calcimimmetics (oral and IV)

#### Status change: all

- Date of transfer to another dialysis facility
- Date of kidney transplantation
- Date of transfer to peritoneal dialysis
- Date of withdrawal from dialysis
- Date of death

The study team will also be collecting and transmitting patient reported outcomes (as well as name and phone number for patients that wish to complete the surveys via telephone) to Northwestern University.

- Kidney Disease and Quality of Life (KDQOL™-36)
- PROMIS Gastrointestinal Belly Pain 5a
- PROMIS Gastrointestinal Constipation 9a
- PROMIS Gastrointestinal Diarrhea 6a
- PROMIS Gastrointestinal Gas and Bloating 13a

- PROMIS Gastrointestinal Nausea and Vomiting 4a
- Name
- Phone Number

#### 5.5 Participant Withdrawal

Participants may decide to withdraw from the study at any time. Patients who initially participate but later elect to withdraw from the trial will have no data transmitted to the DCRI after the date of withdrawal. Additionally, participants who increase dialysis frequency to more than three times weekly, including participants in the high arm who become pregnant, will be withdrawn from the study by the dialysis provider.

Data transmitted to the DCRI prior to withdrawal will remain in the trial database. Contact information for the research personnel from the relevant dialysis provider organization will be available at participating dialysis facilities throughout the duration of the trial to facilitate communication such as a decision to withdraw from the trial. Participants who elect to discontinue phosphate binder medications or protocol-based treatment algorithms will remain as trial participants and continue to have data transmitted to the DCRI unless they withdraw from the trial.

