## 8.2 Statistical Design

In the primary analysis of efficacy, the intention to treat (ITT) sample will be used that includes all randomized patients.

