2. ANALYSIS POPULATIONS

2.1 Definition of Analysis Populations

2.1.1 Intention-To-Treat (ITT) Population

The ITT population will include all patients that have consented to participation in the study. The treatment arms in analyses in the ITT population will be the participant's assigned phosphate target arm, regardless of the participant's actual phosphate levels throughout the course of the trial. The ITT population will be used in the primary analysis of efficacy and all major secondary analyses.

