4.1.2 Censoring Scheme

Primary Censoring Scheme: for time-to-event endpoints, patients will be censored at the earliest of: 1) end of study date, and 2) date of dialysis status change.

End of study date is defined as the earliest of:

- date of withdrawal from study
- date of lost to follow-up
- date of study completion

Date of dialysis status change is the earliest of the following:

- date of transfer to another dialysis facility
- date of kidney transplantation
- date of transfer to peritoneal dialysis
- date of withdrawal from dialysis

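### Follow-up is censored when the provider withdraws a patient for more than three weekly sessions, a post-randomization event; Protocol 5.5, Protocol 4.7.2 and SAP 4.1.2 need reconciling

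*Protocol*

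**What the plan says.** Protocol 5.5 contains three rules that bear on each other.

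- Patients who choose to leave: "Patients who initially participate but later elect to withdraw from the trial will have no data transmitted to the DCRI after the date of withdrawal".
- Provider withdrawal: "participants who increase dialysis frequency to more than three times weekly, including participants in the high arm who become pregnant, will be withdrawn". The provider carries this out, and it is an exit from the study, not only from the arm. The data-stop wording is not repeated here. The section then adds: "Data transmitted to the DCRI prior to withdrawal will remain in the trial database".
- Patients who stop binders or the treatment algorithms stay in the trial and their data keep flowing, unless they withdraw.

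Protocol 4.7.2 deals with patients whom the physician takes off their study arm: "These participants will continue to be followed and will be included in the intent-to-treat analyses".

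SAP 4.1.2 lists "date of withdrawal from study" among the dates that end follow-up. A change in session frequency is not itself a listed status change, so it reaches the analysis only through study withdrawal. Under SAP 4.5.1, two patients who cannot be ranked on death are compared on hospitalizations up to the earlier of their censoring times.

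The analysis set keeps these patients. Protocol 8.2 states that "the intention to treat (ITT) sample will be used that includes all randomized patients"; SAP 2.1.1 states that "The ITT population will include all patients that have consented to participation in the study".

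**The concern.** Moving above three sessions a week happens after randomization and may reflect the patient's condition. The trial is open-label, and the provider who carries out the withdrawal knows the arm. If patients who make the change have a different risk of death or admission from those who do not, censoring them there is informative. If the change is also more common in one arm, the comparison is biased. Both components of the primary endpoint are affected: time to death directly, and the hospitalization count because it is read only to the earlier censoring time of each pair.

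The plan also treats similar situations differently. Leaving the arm or the algorithm leaves follow-up intact, whereas a change in session frequency ends it, and no reason is given. The sentence names pregnancy for the high arm only. It does not say what happens to a pregnant low-arm participant whose frequency does not change.

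The plan has no backstop. SAP 4.1.2 gives one censoring scheme, SAP 5.3 imputes nothing except dates, and the disposition summary in SAP 4.3.1 does not separate provider withdrawals from withdrawals by choice.

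**Working it through.** **Inputs from the documents.** N = 3800, Lo mortality 15% per year, hazard ratio 0.85, hospitalizations 1.8 versus 1.53 per year in susceptible patients, 35% non-susceptible, 5% annual loss (Protocol 8.1); 1:1 allocation and administrative censoring uniform over 2 to 4 years (SAP 1.3); scoring and variance from SAP 4.5.1; two-sided 0.05. **Assumed:** every rate of provider withdrawal and every risk multiple, because the documents give none.

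**1. The plan's own figures.** Simulating the Finkelstein-Schoenfeld test with the Protocol 8.1 inputs gave 98.6% power (1000 runs, mean Z 4.36), in line with the stated figure of above 95%. The mean number of deaths was 1275. For mortality alone, power = Φ(|ln 0.85| × √(1275/4) − 1.96) = Φ(2.90 − 1.96) = 82.7%, in line with the stated 80% or more.

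**2. Shift in the mortality hazard ratio.** Let h = −ln 0.85 = 0.1625 (death), l = −ln 0.95 = 0.0513 (loss), w the rate of change and k the multiple of mortality afterwards. Let A(t) be the probability of not yet being administratively censored: 1 up to 2 years, then (4 − t)/2. Lo mortality is used in both arms.

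- Person-time before the change: ∫ A(t) exp(−(h + l + w)t) dt
- Person-time after it: ∫ A(t) ∫₀ᵗ w exp(−(h + l + w)u) exp(−(kh + l)(t − u)) du dt
- s = after / (before + after)
- Ratio of the censored to the full-follow-up hazard ratio ≈ (1 + s_Lo(k − 1)) / (1 + s_Hi(k − 1))

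| Assumed Hi vs Lo per year | k | s_Hi | s_Lo | Ratio |
|---|---|---|---|---|
| 2% vs 1% | 2 | 0.0504/2.1871 = 2.3% | 0.0255/2.1913 = 1.2% | 1.0116/1.0230 = 0.989 |
| 4% vs 2% | 3 | 0.0857/2.1659 = 4.0% | 0.0438/2.1805 = 2.0% | 1.0401/1.0792 = 0.964 |

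The shifts are about 1.1% and 3.6%. They favour Hi only because Hi was given the higher rate; swapping the rates reverses them.

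**3. Primary test with no true effect.** A different mechanism was simulated here: all provider withdrawals fall in a high-risk 20% of patients, at an overall initial rate of 1% per year in Lo and 2% to 5% in Hi (400 runs each).

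| Risk multiple | Mean Z, as Hi rate goes from 2% to 5% | Rejection rate |
|---|---|---|
| 2-fold | 0.03 to 0.20 | 4.2% to 5.0% |
| 4-fold | 0.07 to 0.34 | 4.8% to 5.8% |

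The Monte Carlo standard error is √(0.05 × 0.95/400) = 1.1 points, so none of these rates can be told apart from 5%. The Z shift moves in the expected direction but is small beside 1.96.

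**4. Power under equal extra withdrawal.** With the planned effect and an extra 1%, 3% or 5% per year in both arms, composite power stayed at about 99% (200 runs each). Deaths fell to 1256, 1223 and 1191, and mortality-alone power to 82.1%, 81.1% and 80.1%.

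**The case against.** Several objections have force.

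- A reader might infer that all data stop for these patients. The explicit sentence, that patients "will have no data transmitted to the DCRI after the date of withdrawal", is written for those who choose to leave. Extending it to provider withdrawal is a reasonable inference, since the next sentence continues the topic and only data sent before withdrawal are said to be kept, but it is not stated. Censoring at withdrawal is stated, and that is enough for the point.
- A reader might infer that intention-to-treat is broken, or that Protocol 4.7.2 is contradicted. Neither follows. No one leaves the ITT set, and 4.7.2 concerns leaving the arm, not the study. What remains is truncated follow-up that fits poorly with 4.7.2.
- A reader might infer that the pregnancy wording makes the rule one-sided. As the sentence is built, pregnancy in the high arm is an instance of the frequency rule, and that rule covers both arms. Pregnancy and planned pregnancy are also exclusions, so few cases are likely. The low-arm case is left unclear, which is a gap in wording.
- A reader might infer a bias toward Hi. Nothing in the documents supports an arm difference, and the opposite direction is equally open.
- SAP 4.1.2 already censors at transplantation, facility transfer and other status changes, so one more censoring event is in keeping with it. But a change in session frequency is not on that list, and such a patient may still be in the same provider's records.

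The small effect on the primary test also stands, and limits how much weight the point can bear.

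**Conclusion.** The point holds as an inconsistency in follow-up rules that creates avoidable and possibly informative censoring. It does not show that the primary result would be materially biased. Direction and size cannot be determined from the documents. Under the assumed scenarios the mortality hazard ratio moves by about 1% to 3.6%, against a planned 15% reduction, and the primary test's rejection rate under no effect stays near 5%. These figures rest on assumed withdrawal rates, an assumed two-to-one imbalance in the hazard-ratio calculation and up to five-to-one in the simulation, and assumed two- to four-fold risks. The change is worth making because it is cheap, not because the expected damage is large.

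**What to change.** Reconcile Protocol 5.5, Protocol 4.7.2 and SAP 4.1.2 as follows.

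- In Protocol 5.5, separate leaving the phosphate target from leaving the study. State that, unless the patient withdraws consent, deaths and hospitalizations continue to be transferred after a change in session frequency or a pregnancy, by the same rule in both arms.
- In SAP 4.1.2, state that this event alone is not a censoring date in the primary analysis.
- In SAP 4.3.1, report these cases by arm, separately from withdrawals by choice.
- Add a sensitivity analysis that censors at the change.

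The cost is protocol and SAP wording and possibly one sentence in the consent form. Protocol 5.4 already draws hospitalizations and deaths from the provider's records, so no new collection is needed while the patient remains with the provider. The trade-off is that some follow-up will be off the assigned target, which an intention-to-treat comparison accepts. The clinical rule on session frequency or pregnancy is left to the provider.

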## 6. POTENTIAL RISKS

## 6.1.1 Breach to Participant Confidentiality

Due to necessity of data merges from with data systems outside the enrolling site, breach to confidentiality is a potential risk. To minimize this risk, primary identifiers will be retained only within the data systems where required to conduct the study; these will be omitted as data travel downstream and only study IDs will be in the analysis datasets. Further deidentification and anonymization methods will be used when making data available for outside investigators. DCRI is part of the Duke HIPAA covered entity and has experience working with PHI in the research context; DCRI is extremely prudent in keeping patient data secure and confidential.

## 6.1.2 Risks Related to Hyperphosphatemia Management

Observational studies have linked hyperphosphatemia in patients with ESRD to increased risks of CVD and death. Phosphate binders are the mainstay of management of hyperphosphatemia in patients undergoing dialysis treatment. Use of these medications can lead to gastrointestinal side effects, including nausea, vomiting, abdominal pain, bloating, dyspepsia, diarrhea, and constipation. Use of calcium-based phosphate binders can also lead to hypercalcemia. It is anticipated that gastrointestinal side effects will be reduced in the high phosphate target arm and they will remain similar to pre-intervention levels in the low phosphate target arm. Risks related to hyperphosphatemia management in both arms will be managed according to usual clinical care, which typically entails adjustment of phosphate binder dose and/or substitution of drug class.

## 7. SAFETY ASSESSMENTS

## 7.1 Adverse Event Reporting and Follow-up

Among patients undergoing hemodialysis, adverse events of moderate or higher severity are extremely common and usually result in hospitalization (or death). Based on this information, and given that hospitalization is the primary outcome of HiLo, additional information on adverse events will not be collected. Periodically reports will be generated related to laboratory-based events and allow the DSMB to review in a blinded manner the rates of these events in high versus low target groups. All laboratory parameters are measured either monthly or quarterly for all patients as part of routine clinical care:

- Hypophosphatemia, defined as serum phosphate <2.0 mg/dL;
- Hyperphosphatemia, defined as serum phosphate >7.5 mg/dl;
- Hypercalcemia, defined as total uncorrected serum calcium >10.5 mg/dL;
- Excessive iron supplementation, defined as serum ferritin >1000 ng/ml and transferrin saturation (TSAT) >50% (to assess for the potential effects of excess iron-based binder use); and
- Secondary hyperparathyroidism, defined as parathyroid hormone (PTH) levels 9 times the upper limit of normal for the assay, based on the threshold articulated in the international KDIGO guidelines.

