4.6.2 Clinical Safety Laboratory Events

Laboratory measurements are collected either monthly or quarterly for all patients as part of routine clinical care. Predetermined laboratory safety events will be collected. Below are defined the laboratory events of interest in HiLo:

- Hypophosphatemia, defined as serum phosphate <2.0 mg/dL
- Hyperphosphatemia, defined as serum phosphate >7.5 mg/dL
- Hypercalcemia, defined as total uncorrected serum calcium >10.5 mg/dL
- Excessive iron supplementation, defined as serum ferritin >1000 ng/mL and transferrin saturation (TSAT) >50%
- Secondary hyperparathyroidism, defined as parathyroid hormone (PTH) levels greater than 9 times the upper limit of normal for the assay

A listing of laboratory safety events will be created, along with a table of counts of each type of event by treatment group.

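### The laboratory safety list counts high calcium but not low calcium, and neither document specifies a by-arm calcium summary

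*Protocol*

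**What the plan says.** Protocol 7.1 and SAP 4.6.2 name five laboratory events: low phosphate, high phosphate, high calcium, excess iron and high PTH. Phosphate has a row at each end: "Hypophosphatemia, defined as serum phosphate <2.0 mg/dL" and "Hyperphosphatemia, defined as serum phosphate >7.5 mg/dL". Calcium has one row, the same in both documents: "Hypercalcemia, defined as total uncorrected serum calcium >10.5 mg/dL".

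The planned output is limited to these events. SAP 4.6.2 states: "A listing of laboratory safety events will be created, along with a table of counts of each type of event by treatment group". The laboratory reports to the DSMB (Protocol 7.1) cover the rates of the same events. Beyond them, "additional information on adverse events will not be collected". The analyses in SAP 4.5 do not include calcium.

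Three other places bear on which way calcium might move:
- Protocol Table 2 and section 4.6.5 describe less intensive phosphate control in the Hi arm, with binder therapy reduced below the lower threshold.
- Protocol 6.1.2 says: "Use of calcium-based phosphate binders can also lead to hypercalcemia".
- Protocol 4.6.6 allows diet to be liberalized in the Hi arm, with dairy as the example.

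**The concern.** A row with only an upper cut-off can register a downward shift in calcium in one way: as fewer events. If the Hi strategy lowered calcium, the DSMB and the final report would see the favourable end of that shift, and no row would count the unfavourable end. The list already anticipates effects of binder exposure, since high calcium and excess iron both fit over-treatment. The possible effect on calcium of reducing calcium-based binders, which is part of the experimental strategy, has no row.

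This matters more here than in a trial with ordinary adverse event reporting, because the laboratory list is the only prespecified safety output apart from deaths and hospitalizations. The primary efficacy result is not affected.

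**Working it through.** **Step 1. What is counted.** There is no stated figure to reproduce: neither document gives an expected calcium event rate. The two lists agree.

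| Analyte | Low-side event | High-side event |
|---|---|---|
| Phosphate | <2.0 mg/dL | >7.5 mg/dL |
| Calcium (total, uncorrected) | none | >10.5 mg/dL |
| PTH | none | >9 times the upper limit of normal |
| Ferritin with TSAT | none | >1000 ng/mL with >50% |

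**Step 2. Is a downward shift plausible?** The Hi arm has less intensive binder treatment (Protocol Table 2, 4.6.5), and calcium-based binders can raise calcium (Protocol 6.1.2). Together these point to lower calcium in the Hi arm. Against this, more dairy (4.6.6) may raise it. Binder class is left to local providers (4.6, 4.6.2), and the share of patients on calcium-based binders is not given. The direction is plausible but not established.

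**Step 3. Are the data available?** Yes. Protocol 5.4 has all available calcium and albumin values transferred monthly.

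**Step 4. Illustration on assumed inputs.** The mean, SD, shift and low cut-offs below are assumptions, not taken from the documents. The cut-offs 8.0 and 7.5 serve only to show the lower tail and are not proposals. Let calcium be normal with mean m and SD s in the Lo arm and mean m − d in the Hi arm. Then

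- share above 10.5 = 1 − Φ((10.5 − mean)/s)
- share below c = Φ((c − mean)/s)

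Central case, m = 9.0, s = 0.7, d = 0.2:

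| Tail | Lo arm z | Lo arm share | Hi arm z | Hi arm share | Has a row in the plan? |
|---|---|---|---|---|---|
| >10.5 | 2.14 | 1.6% | 2.43 | 0.8% | Yes |
| <8.0 | −1.43 | 7.7% | −1.14 | 12.7% | No |
| <7.5 | −2.14 | 1.6% | −1.86 | 3.2% | No |

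Grid: m = 8.8, 9.0, 9.2; s = 0.6, 0.7; d = 0.1, 0.2, 0.3 (18 combinations).

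| Quantity | Smallest | Largest |
|---|---|---|
| Absolute fall in values >10.5 | 0.1 points (m 8.8, s 0.6, d 0.1) | 2.1 points (m 9.2, s 0.7, d 0.3) |
| Relative fall in values >10.5 | 28% (m 9.2, s 0.7, d 0.1) | 81% (m 8.8, s 0.6, d 0.3) |
| Absolute rise in values <8.0 | 1 point (m 9.2, s 0.6, d 0.1) | 11 points (m 8.8, s 0.6 or 0.7, d 0.3) |

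For a uniform downward shift the direction does not depend on m or s: the reported tail shrinks and the unreported tail grows. If d = 0, neither tail changes. If calcium rises in the Hi arm, the existing row records the increase.

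**The case against.** The strongest case against has five parts.

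1. **The table is not slanted towards the Hi arm as a whole.** A reader might infer that it can show only benefit. That is wrong: the high-phosphate row and the PTH row ("Secondary hyperparathyroidism, defined as parathyroid hormone (PTH) levels greater than 9 times the upper limit of normal for the assay") can both show Hi-arm harm, and a raised PTH may be an indirect sign of low calcium. The point is therefore confined to the calcium row. PTH does not substitute for it: it is nonspecific, collected every three months (Protocol 5.4), and itself a target of treatment.

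2. **Other data could reveal low calcium.** Protocol 1.2 foresees a merge with Medicare claims giving hospitalization codes, and SAP 1.4 says that cause-specific hospitalization data will be collected for Medicare beneficiaries. Coded admissions could be searched, so it would be wrong to say that nothing could catch the low end. But no calcium-specific analysis of these data is planned, and low values that lead to no admission would not appear in them.

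3. **A fall in calcium is not stated anywhere.** This stands. A reader might also take Protocol 4.6.7 as evidence that rising PTH in the Hi arm would be met by cutting calcium intake. The passage reads "altering the binder regimen to reduce calcium intake, or using calcimimetics or vitamin D analogs to lower PTH". It describes usual care in both arms, the calcium-intake example fits hypercalcemia rather than PTH, and vitamin D analogs are among the options. It does not support a fall specific to the Hi arm.

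4. **The illustration considers only downward shifts.** This also stands. It shows what the list would miss if calcium fell, not how likely a fall is.

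5. **Unseen documents may cover the gap.** Protocol 9.1 refers to a DSMB charter, and SAP 7 to a separate output document that may be updated. Either might add calcium summaries. Nothing in the protocol or SAP commits to one.

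**Conclusion.** The point holds as an asymmetry in the safety list: calcium is counted above 10.5 mg/dL only, and no low-calcium event or by-arm calcium summary is specified. If the Hi strategy lowers calcium, the calcium row can show only fewer Hi-arm events, and no prespecified safety output counts the low values.

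The size cannot be derived from the documents. On the assumed grid, a reported fall of 0.1 to 2.1 percentage points above 10.5 (28% to 81% relative) accompanies an unreported rise of 1 to 11 points below 8.0. These figures rest wholly on normality, the assumed means and SDs, and a uniform downward shift of 0.1 to 0.3 mg/dL. The documents do not show that calcium will fall, that low calcium would be undetectable, or that the safety table as a whole is biased. This is a worthwhile, inexpensive improvement to safety monitoring, not a demonstrated bias.

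**What to change.** In Protocol 7.1 and SAP 4.6.2:
- Add a low-calcium laboratory event on the same monthly total calcium, with a cut-off that the sponsor fixes before by-arm data are seen.
- Add to the DSMB and final safety tables a by-arm summary of calcium over time: mean, lower percentiles and upper percentiles.
- Show that summary alongside albumin, or also in albumin-corrected form. The trial hypothesizes higher albumin in the Hi arm (Protocol 2.1), which could mask a fall when calcium is uncorrected.

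The cost is one more event row and one more table for the DSMB to read. Calcium and albumin are already transferred, so no new data are needed, and no treatment rule or efficacy analysis changes.
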